6.5.2 Secondary Endpoints

6.5.2.1 Disease Control Rate (DCR)

DCR is defined as the proportion of patients who achieve a confirmed CR or PR according to RECIST v1.1 as assessed by the investigator, or meet the SD criteria at least once after start of study treatment at a minimum interval of 5 weeks. Patients who do not have at least 1

post-baseline response assessment or patients whose response cannot be assessed will be counted as not achieving disease control.

As an exploratory analysis, DCR will also be calculated without requiring confirmation of CR or PR for disease control.

DCR will be estimated for each cohort and its exact 2-sided 90% CIs will be calculated.

6.5.2.2 Duration of Response (DOR)

DOR is defined as the time from the first documentation of objective response (CR or PR that is subsequently confirmed) to the first documentation of PD or death due to any cause, whichever comes first. PD includes radiologic evidence of tumor progression and clinical progression per investigator.

Patients who are not evaluable or have a response of SD or better per RECIST v1.1 at the same visit as investigator claim of clinical progression will be counted as disease progression (i.e., an event). The date of progression will be the date of investigator claim of clinical progression or PD date per RECIST v1.1, whichever is earlier.

DOR data will be censored as described below:

- Patients who do not have PD and are still on study at the time of an analysis will be censored at the date of last disease assessment documenting absence of PD.
- Patients who have started a new anticancer treatment prior to documentation of PD will be censored at the date of last disease assessment prior to the start of new treatment.
- Patients who are removed from the study prior to documentation of PD will be censored at the date of last disease assessment documenting absence of PD.

DOR will only be calculated for patients who achieve a confirmed CR or PR.

DOR will be analyzed by cohort using the Kaplan-Meier methodology and Kaplan-Meier plots will be provided. The median DOR and its 2-sided 90% CI will be calculated as appropriate.

Sensitivity analyses will be performed for DOR to evaluate the robustness of treatment effects:

- A sensitivity analysis will be performed by censoring deaths or PD per RECIST v1.1 occurring after two or more missed visits at the last disease assessment;
- Another sensitivity analysis will be performed by counting PD or Death which occurred after start of new anti-cancer as events;
-

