2. OBJECTIVES

This study will evaluate the efficacy, safety, and pharmacokinetics (PK) of LV in subjects with solid tumors. Specific objectives and corresponding endpoints for the study are summarized in [Table 7](#).

Table 7: Objectives and corresponding endpoints

Primary Objective	Corresponding Primary Endpoint

 Evaluate antitumor activity of LV as monotherapy (Part A, Part B, and Part C Arm 1 [Cohort 8 only]) and in combination with pembrolizumab (Part C Arm 2 and Arm 3, Cohort 8 only) 	
 Investigator-determined confirmed ORR as measured by RECIST v1.1 for all tumor types For prostate cancer, investigator-determined PSA response by Prostate Cancer Clinical Trials Working Group 3 (PCWG3) criteria in addition to ORR
Secondary Objectives	Corresponding Secondary Endpoints

 Evaluate the safety and tolerability of LV as monotherapy (Part A, Part B, and Part C Arm 1 [Cohort 8 only]) and in combination with pembrolizumab (Part C Arm 2 and Arm 3, Cohort 8 only) Evaluate stability and control of disease Evaluate durability of response in subjects who respond to LV as monotherapy (Part A, Part B, and Part C Arm 1 [Cohort 8 only]) and in combination with pembrolizumab (Part C Arm 2 and Arm 3, Cohort 8 only) Evaluate PFS of subjects treated with LV as monotherapy (Part A, Part B, and Part C Arm 1 [Cohort 8 only]) and in combination with pembrolizumab (Part C Arm 2 and Arm 3, Cohort 8 only) Evaluate survival of subjects treated with LV as monotherapy (Part A, Part B, and Part C Arm 1 [Cohort 8 only]) and in combination with pembrolizumab (Part C Arm 2 and Arm 3, Cohort 8 only) Assess PK of LV (Parts A-C) Assess immunogenicity of LV (Parts A-C) 	
 Type, incidence, severity, seriousness, and relatedness of AEs Investigator-determined DCR as measured by RECIST v1.1 Investigator-determined DOR as measured by RECIST v1.1 for all tumors For prostate cancer, investigator-determined PSA-DOR Investigator-determined PFS as measured by RECIST v1.1 for all tumors For prostate cancer, investigator-determined PSA-PFS OS Selected PK parameters for LV, total antibody, and MMAE Incidence of ATAs to LV
Additional Objectives	Corresponding Additional Endpoints

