7.2. Response/Efficacy Assessments

The determination of antitumor activity will be based on objective response assessments made by the investigator according to the RECIST v1.1 ([Appendix H](#)) ([Eisenhauer 2009](#)) and treatment

decisions by the investigator will be based on these assessments for Parts A–C (Arm 1 only). For subjects in Part C (Arms 2 and 3), treatment decisions by the investigator will be based on iRECIST (see [Appendix I](#)) ([Seymour 2017](#)). Clinical response of CR, PR, SD, or PD will be determined at each assessment. In addition, images will be collected by an independent review facility for possible future analysis.

For non-prostate cancer subjects, responses (CR or PR) will be confirmed 4–6 weeks after first documentation of response.

For all subjects, tumor imaging should also be performed whenever disease progression is suspected.

Measures of anticancer activity will be assessed by either CT with contrast or MRI scans at protocol-specified time points. A diagnostic quality CT is required unless medically contraindicated.

For prostate cancer subjects, PSA response is defined as a reduction from baseline PSA level of at least 50%, maintained for at least 3 weeks. The duration of PSA response is defined as the time between the first evaluation at which the response criteria are met and the first documentation of PSA progression. Early increase in PSA within 12 weeks, when followed by subsequent decline, is ignored in determining this endpoint.

For subjects unable to tolerate contrast-enhanced CT assessments, MRI imaging is acceptable. MRI scans may not be appropriate to assess lung parenchymal lesions and CT without contrast enhancement is acceptable in such situations. **Subjects must be evaluated with the same imaging modality throughout the study for efficacy assessments.** If any other radiographic or disease assessment examination is conducted per standard of care, the assessment information will be collected in the CRF.

Further details are provided in the study imaging manual.

Tumor assessments will continue until the subject has radiologically-confirmed disease progression per RECIST v1.1 by the investigator according to Sections [6.4](#), [6.6](#), and [6.7](#). Subjects who discontinue study treatment for reasons other than objective disease progression by RECIST v1.1 (see [Appendix H](#)) will continue to receive tumor assessments according to Section [6.7](#).

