9.2.4. Duration of Response

DOR is defined as the time from the first documentation of objective response (CR or PR that is subsequently confirmed) to the first documentation of PD or death due to any cause, whichever comes first.

DOR data will be censored as described below:

- Subjects who do not have PD and are still on study at the time of an analysis will be censored at the date of last disease assessment documenting absence of PD.
- Subjects who started a new anticancer treatment prior to documentation of PD will be censored at the date of last disease assessment prior to the start of new treatment.
- Subjects who are removed from the study prior to documentation of PD will be censored at the date of last disease assessment documenting absence of PD.

DOR will only be calculated for subjects who achieve a confirmed CR or PR as measured by RECIST v1.1 for all tumors.

PSA-DOR is defined as the time from the first documentation of PSA response (subsequently confirmed at least 3 weeks apart) to the first documentation of PSA progression or death due to any cause, whichever comes first.

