9.2.5. Progression-Free Survival

Progression-free survival (PFS) is defined as the time from the start of study treatment to the first documentation of PD by RECIST v1.1 or clinical PD or by PSA progression (prostate cancer cohort) or death due to any cause, whichever comes first. PSA-PFS is defined in Section [9.2.7](#).

The same censoring rules as outlined in Section [9.2.4](#) for DOR will be applied to PFS. Subjects lacking an evaluation of tumor response after their first dose of study drug will have their event time censored at Day 1.

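### Duration of response and PFS are labelled RECIST v1.1 endpoints, but the event definitions add clinical progression and no RECIST-only analysis is planned

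*SAP*

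**What the plan says.** **Labels.** Protocol Section 2, Table 7 lists the secondary endpoints as "Investigator-determined DOR as measured by RECIST v1.1 for all tumors" and "Investigator-determined PFS as measured by RECIST v1.1 for all tumors". PSA-based DOR and PSA-based PFS are separate entries for prostate cancer. SAP Table 2-1 gives DOR and PFS the same RECIST label.

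**DOR events.** Protocol 9.2.4 runs DOR "to the first documentation of PD or death due to any cause, whichever comes first" and does not say what PD comprises. SAP 6.5.2.2 does: PD is radiologic progression or clinical progression per the investigator. A responder whose scan is not evaluable, or still shows stable disease or better, "at the same visit as investigator claim of clinical progression will be counted as disease progression (i.e., an event". Progression is dated at the earlier of the clinical claim and RECIST PD.

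**PFS events.** Protocol 9.2.5 counts "PD by RECIST v1.1 or clinical PD or by PSA progression (prostate cancer cohort) or death due to any cause, whichever comes first". SAP 6.5.2.3 says PD or death. It takes the censoring rules and sensitivity analyses from the DOR section, but does not restate the rule on clinical progression.

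**PSA response duration.** Protocol 7.2 defines it as the time between "the first evaluation at which the response criteria are met and the first documentation of PSA progression". Protocol 9.2.4 runs it "to the first documentation of PSA progression or death due to any cause".

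**The concern.** A reader who sees an endpoint labelled RECIST expects events that rest on measured lesions or death. Here a patient whose scan shows a continuing partial or complete response can be counted as having ended that response on the investigator's clinical judgement, in an open-label study with investigator assessment throughout. Two programmers working from different sections could produce different event counts, dates and medians, and each could cite the documents.

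The mismatch does not come from the SAP having been written for the 2019 protocol. Each document disagrees with itself: Table 7 against 9.2.5 in the protocol, and Table 2-1 against 6.5.2.2 in the SAP.

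What is at stake is the meaning and the value of the Kaplan-Meier medians for DOR and PFS. The primary response rate, the futility rule and the sample size do not use these endpoints.

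**Working it through.** **1. One test case, read against each section.** A confirmed responder is called clinically progressing at a visit where the scan still shows partial response. No RECIST PD or death has occurred.

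| Section | DOR event? | PFS event? |
|---|---|---|
| Protocol Table 7 | no | no |
| Protocol 9.2.4 | not determined (PD unqualified) | – |
| Protocol 9.2.5 | – | yes |
| SAP Table 2-1 | no | no |
| SAP 6.5.2.2 | yes, dated at the claim | – |
| SAP 6.5.2.3 | – | not stated |

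**2. Is a RECIST-only result planned anywhere?** SAP 6.5.2.2 words two sensitivity analyses. One censors deaths or RECIST PD that follow two or more missed visits. The other keeps events that occur after new therapy has started. Neither removes clinical progression from the event. The list ends in an empty bullet in the text available, and nothing here rests on it.

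**3. Prostate cohort.** Protocol 9.2.5 puts PSA progression into PFS, while Table 7 lists PSA-PFS separately (defined in 9.2.7). Protocol 4.1 allows up to 15 subjects with non-measurable disease, and Appendix L gives PCWG3 bone progression criteria, but 9.2.5 does not say whether bone progression is a PFS event.

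**4. Is there a plan figure to reproduce?** No stated figure depends on DOR or PFS. For context, the N=30 exact intervals in protocol 9.1 reproduce: 6/30 gives (9.1%, 35.7%) against the printed (9%, 36%).

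**5. Size on the DOR curve.** Assume a 20% response rate: 0.20 × 30 = 6 responders, all eventually with an event. Let the first event be a clinical claim that a RECIST-only analysis censors.

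| After event | Clinical PD counted | RECIST-only | Gap (points) |
|---|---|---|---|
| 1st | 5/6 | 1 | 16.7 |
| 2nd | 4/6 | 4/5 | 13.3 |
| 3rd | 3/6 | 3/5 | 10.0 |
| 4th | 2/6 | 2/5 | 6.7 |
| 5th | 1/6 | 1/5 | 3.3 |

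**6. Size on a median.** The documents give no share of clinical-only progression, so call it f. Assume constant hazards and independent censoring of those events. The composite hazard is λ = ln 2 / m and the RECIST-or-death hazard is (1 − f)λ, so the RECIST-only median is m / (1 − f).

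- f = 5%, 10%, 20%, 30% gives ratios of 1.05, 1.11, 1.25 and 1.43.
- For scale, take m = 2.9 months, the DOR that protocol Table 4 reports at 1.25 mg/kg q1wk in the breast cancer study. The RECIST-only medians are then 3.05, 3.22, 3.62 and 4.14 months.
- Simulation of 200,000 subjects gave 3.20, 3.62 and 4.15 months at f = 10%, 20% and 30%.

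**7. PSA response duration.** If a share q of terminal events are deaths without PSA progression, censoring them multiplies the median by 1 / (1 − q) under the same assumptions: 1.11 at q = 10% and 1.25 at q = 20%. Both values of q are assumed.

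**The case against.** The strongest reply is that this is a labelling matter on secondary, descriptive endpoints, and that protocol 9.3 leaves detail to the SAP. That explains why 9.2.4 leaves PD unqualified. It does not explain a SAP that contradicts its own Table 2-1, or a protocol whose PFS definition differs from its Table 7.

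A second reply is that RECIST-only is not clearly better. Protocol 7.2 continues scans after a stop for reasons other than RECIST PD, but 6.7 ends them at new anticancer therapy or investigator decision. Patients called clinically progressing are likely to start new therapy and would be censored, possibly informatively. This stands: either definition can be the main one, provided that it is stated.

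A third is that 9.2 is the definitions section, so its inclusion of death governs PSA response duration. That is probably the intent, and 7.2 should then say the same.

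Some stronger readings are tempting but unsupported:

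- **Arm-dependent bias in Part C.** A reader might infer this because Arms 2 and 3 judge clinical stability before treating past progression. In 7.2 that judgement follows a RECIST v1.1 PD, which is already an event under every definition here, so it cannot create or advance one.
- **Dates shift by at most one scan interval.** Imaging on suspicion of progression can shorten the gap, and RECIST PD may come several scans later or never.
- **17 points throughout the curve.** It is the gap at the first event only (working, step 5).
- **The same-visit rule governs PFS.** It is written only in the SAP's DOR section.

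**Conclusion.** The point holds and merits a correction. DOR and PFS carry a RECIST label, while protocol 9.2.5 (PFS) and SAP 6.5.2.2 (DOR) define a wider event. No RECIST-only analysis is specified, so following those two sections never yields the labelled endpoint. For PFS the SAP leaves the choice open: reading its PD as RECIST-only would match the label but contradict 9.2.5.

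The size is uncertain because the frequency of clinical-only progression is not given. About 17 points at the first event applies to six responders with that event reclassified. The median ratios of 1.05 to 1.43 rest on assumed shares of 5% to 30%, constant hazards and independent censoring. They would be smaller if scans continue to RECIST PD soon after the clinical claim, and could differ if censoring is informative. No test or decision threshold changes.

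**What to change.** State one event definition per endpoint, in identical words in protocol Table 7, 9.2.4 and 9.2.5, and in SAP Table 2-1, 6.5.2.2 and 6.5.2.3. Two versions are acceptable:

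- **RECIST main analysis.** The event is RECIST v1.1 PD or death, as labelled, with RECIST PD, clinical PD or death as a named sensitivity analysis.
- **Composite main analysis.** Clinical PD stays in the event, the endpoint is relabelled accordingly, and a RECIST-only analysis is added by name.

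In either case:

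- Say whether the same-visit and earlier-date rules apply to PFS.
- For the prostate cohort, say whether PSA progression and PCWG3 bone progression are PFS events, given the separate PSA-PFS endpoint. A plain switch to RECIST PD or death would drop PSA progression without comment.
- Align protocol 7.2 with 9.2.4 so that death ends PSA response duration.

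The cost is wording and one extra table per endpoint. The SAP still follows the original 2019 protocol and has no prostate cohort, so it needs revision anyway. The downside is that the RECIST-only analysis censors subjects with clinical PD who start new therapy, possibly informatively. Reporting both analyses makes any difference visible.

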5.4.4. Prohibited Concomitant Therapy

No other investigational drug, immunosuppressive medication, non-study systemic antineoplastic therapy, or approved anticancer treatment is permitted during the treatment period, including chemotherapy, endocrine therapy, biological response modifiers, surgery, immunotherapy, or radiotherapy (except palliative radiotherapy, see Section 5.4.2.3). Concurrent participation in another clinical trial of a medical intervention is not allowed.

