6.7. Follow-up

All subjects will be followed for survival until death or study closure, whichever occurs first. Survival and subsequent anticancer therapy follow-up may be conducted with clinic visits or telephone calls.

For subjects who discontinue study treatment for reasons other than progression, the following assessments will be conducted every 6 weeks (± 3 days) for 12 months after the first dose of LV and every 12 weeks (± 7 days) thereafter, until disease progression, initiation of a new anticancer therapy, investigator decision, consent withdrawal, study termination by the sponsor, pregnancy, or death, whichever comes first:

- Physical examination (see Section [7.6.4](#))
- Pregnancy test for subjects of childbearing potential 24 weeks after the last dose of LV (see Section [7.6.5](#))
- CT/MRI scan (see Section [7.2](#) for details); after a year of follow-up, reduce frequency to institution's standard of care
- In subjects who discontinue study treatment due to pregnancy, response assessments should be conducted as appropriate

For prostate cancer subjects who discontinue study treatment for reasons other than progression, the following assessments will be conducted until disease progression, initiation of a new anticancer therapy, investigator decision, consent withdrawal, study termination by the sponsor, or death, whichever comes first:

- Physical examination every 12 weeks (± 7 days) (see Section [7.6.4](#))
- PSA assessment every 12 weeks (± 7 days)
- Bone scan every 12 weeks (± 7 days) (see Section [7.2.1](#))
- Soft tissue tumor assessment (CT/MRI) every 12 weeks (± 7 days) until disease progression for subjects with measurable disease

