6.5.2.3 Progression-Free Survival (PFS)

PFS is defined as the time from the start of study treatment to the first documentation of PD or death due to any cause, whichever comes first.

The same censoring rules as outlined in Section 6.5.2.2 for DOR will be applied to PFS. Patients lacking an evaluation of tumor response after their first dose of study drug will have their event time censored at Day 1.

PFS will be analyzed by cohort using the Kaplan-Meier methodology and Kaplan-Meier plots will be provided. The median PFS and its 2-sided 90% CI will be calculated as appropriate. The PFS rates at 3 and 6 months, and every 3 months thereafter, will be reported and their 2-sided 90% CIs will be calculated.

Sensitivity analysis of PFS will be performed as described in Section 6.5.2.2 for DOR.

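### The DOR and PFS sensitivity analysis for new anticancer therapy needs progression data that Protocol 6.7 stops scheduling, so mostly deaths are added and agreement with the main result does not show robustness

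*SAP*

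**What the plan says.** **Main rule.** Under SAP 6.5.2.2, a patient who begins another anticancer treatment before PD is documented "will be censored at the date of last disease assessment prior to the start of new treatment". SAP 6.5.2.3 uses the same censoring for PFS.

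**Check on that rule.** SAP 6.5.2.2: "Another sensitivity analysis will be performed by counting PD or Death which occurred after start of new anti-cancer as events". SAP 6.5.2.3: "Sensitivity analysis of PFS will be performed as described in Section 6.5.2.2 for DOR".

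**What is collected.** Protocol 5.4.4: "No other investigational drug, immunosuppressive medication, non-study systemic antineoplastic therapy, or approved anticancer treatment is permitted during the treatment period". New therapy therefore normally starts after study treatment has ended. Protocol 7.2 says that subjects who stop treatment without objective PD "will continue to receive tumor assessments according to Section" 6.7. Section 6.7 runs those assessments "until disease progression, initiation of a new anticancer therapy, investigator decision, consent withdrawal, study termination by the sponsor, pregnancy, or death, whichever comes first". It also says: "All subjects will be followed for survival until death or study closure, whichever occurs first". Contact about subsequent therapy continues as well.

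**The concern.** The check is meant to show whether censoring at new therapy flatters DOR and PFS. Censoring is harmless if switching is unrelated to prognosis. It is optimistic if patients switch because they are getting worse. To separate the two, the check needs the date of progression after the switch, and Section 6.7 stops the scheduled scans at that moment. Death is the only later event collected systematically.

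A patient who progresses after switching and later dies therefore enters with the death date in place of the PD date. For a patient who switches and is still alive with no recorded PD, the SAP does not say where the sensitivity analysis censors. The risk is that a result close to the main one is reported as support for durability.

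**Working it through.** The documents give no figure for this analysis, so there is none to reproduce. The check is a reading of the passages, a small worked example and simulations on assumed inputs.

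**1. Passages side by side.**

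| Needed by the check | Collected after new therapy starts |
|---|---|
| PD date | No scheduled scan (Protocol 6.7) |
| Death date | Yes, to death or study closure (Protocol 6.7) |
| Start date of new therapy | Yes (Protocol 6.7); a missing day is imputed (SAP Appendix B) |

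**2. Worked example (invented data).** Four patients have PD at 2, 4, 6 and 8 months. A fifth is last scanned at 2.8, starts new therapy at 3 and truly progresses at 3.2, unseen. The Kaplan-Meier estimate multiplies (1 − 1/number at risk) at each event.

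- Truth, event at 3.2: 0.80, 0.60, then 0.40 at month 4. Median 4.
- Main rule, censored at 2.8: 0.80; 0.80 × 2/3 = 0.53 at month 4; 0.53 × 1/2 = 0.27 at month 6. Median 6.
- SAP check, death at 3.5: 0.40 at month 4. Median 4.
- SAP check, death at 5: 0.60 at month 4, 0.40 at month 5. Median 5.
- SAP check, death at 10: 0.60 at month 4, 0.40 at month 6. Median 6, with a curve above the main one at month 6 (0.40 against 0.27).
- Therapy start as event, at 3: 0.80, 0.60, then 0.40 at month 4. Median 4.

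The same unseen progression gives a check below the main result or level with it at the median, depending only on when the patient dies.

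**3. Simulated medians (months).** Assumptions, none from the documents: exponential time to PD with median 4.0; 18-month cutoff; no PD captured after the switch; survivors after the switch censored as in the main analysis. Informative switching means 0 to 2 months before PD.

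| Switching; median PD to death | Share switching | Main | SAP check | Therapy start as event |
|---|---|---|---|---|
| Independent of PD; 6–10 | 10% | 4.0 | 4.1 | 3.6 |
| | 20% | 4.0 | 4.2–4.3 | 3.2 |
| | 30% | 4.0 | 4.4–4.5 | 2.8 |
| Informative; 6–10 | 10% | 4.4 | 4.5 | 3.9 |
| | 20% | 4.9 | 5.0 | 3.8 |
| | 30% | 5.4–5.5 | 5.6–5.7 | 3.7 |
| Informative; 3 | 30% | 5.4 | 5.2 | 3.7 |

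**4. Wider grid.** This used 72 scenarios with 6-weekly scans. Median time to PD was 3 or 6 months, later survival 3, 8 or 12 months, and 10, 20 or 40% switched. Minimum follow-up was 6 months (the SAP 5.10 minimum) or 24. The measure is mean PFS restricted to 12 months; differences within 0.03 month count as the same.

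| Survivors censored at | Check compared with | Longer | Same | Shorter | Range of difference (months) |
|---|---|---|---|---|---|
| Last scan before therapy | Continued scans | 65 | 6 | 1 | −0.03 to +1.76 |
| Data cutoff | Continued scans | 72 | 0 | 0 | +0.05 to +2.06 |
| Last scan before therapy | Main analysis | 23 | 12 | 37 | −0.87 to +1.07 |
| Data cutoff | Main analysis | 44 | 9 | 19 | −0.75 to +1.45 |

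The unstated censoring point alone changes how often the check exceeds the main analysis, from 23 to 44 of 72 scenarios.

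**5. Why therapy start gives a lower bound.** For each switcher the therapy start precedes the later PD or death, so the event time cannot exceed the true one.

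**The case against.** **Some PD after new therapy can still be captured.** Footnote f of the treatment schedules (Protocol Appendices B, C and D) names only progression as the end of assessment. Protocol 7.2 records standard-of-care examinations in the CRF. SAP 6.5.2.2 accepts clinical progression, which needs no scan. Protocol 6.6 asks for the end-of-treatment visit, with imaging unless recently done, before a new therapy, so PD at the switch will often be caught. All of this stands and reduces the number of patients affected. None of it makes later PD collection systematic, and footnote f conflicts with the stop rule in 6.7.

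**The check can expose optimism.** In one grid scenario (median time to PD 6 months, later survival 3 months, 40% switching shortly before PD, 6-month follow-up) the main median is 9.7 months. The check gives 7.4 or 7.9 and continued scans give 6.9. This also stands. A reader might infer that the check necessarily makes DOR and PFS look longer, or can never reveal optimism. The documents do not support that: the direction against the main analysis depends on survival after the switch, which they do not give.

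**Therapy start as the event is itself biased.** With 30% switching independently of PD it gives 2.8 against a true 4.0, a larger error than the check's 4.4 to 4.5. That is a reason to add it as a bound and not to substitute it.

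**Versions.** The SAP is written to the original protocol of 22 April 2019 and covers Cohorts 1 to 6. The stop rule quoted is in Amendment 04, and the original follow-up rule is not visible. The mismatch is therefore between the two current documents, and says nothing about PSA endpoints, which this SAP does not contain.

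**Conclusion.** The concern holds in a limited form. The written check relies on progression dates that Protocol 6.7 does not schedule, so it adds mainly deaths and cannot properly test the censoring rule. Against true progression it was too long in nearly all scenarios run: by about 0.1 to 1.7 months at the median in the 4.0-month illustration, with one negligible reversal (−0.03 month) in the wider grid. Against the main analysis it may be longer, the same or shorter. Agreement between the two is therefore uninformative. When switching is informative and survival after PD is 6 to 10 months, the check lies close to an already optimistic main result.

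These sizes rest on an assumed share switching, an assumed survival after PD and no PD captured after the switch; any PD that is captured shrinks them. The affected results are secondary and descriptive, in cohorts of at most 30. The confirmed ORR is untouched.

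**What to change.** In SAP 6.5.2.2 and 6.5.2.3:

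- Keep the written analysis. State that PD after new anticancer therapy is not systematically collected, and specify the censoring date for patients who switch and have no later event.
- Add an analysis of DOR and PFS in which the start of new anticancer therapy before documented PD is the event date. Label it a conservative lower bound and show it beside the main result.
- Report, per cohort, the number of patients who started new therapy before PD. If few did, the question closes itself.

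In the protocol, reconcile the end of tumour assessment in Section 6.7 with footnote f of the schedules.

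The SAP cost is a few sentences and one extra run on dates already collected and imputed, with no added scans. The added estimate will look less favourable, materially so if many switch: about 2.8 against 4.0 months, or 1.2 months lower, if 30% switch independently of PD (assumed figures).
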